### ***Peginterferon lambda therapy in chronic viral hepatitis***

IFN-lambda is a type III of IFN with different structural features, receptor characteristics, and biological activities than IFN- $\alpha$  (Type I). IFN-lambda was first reported in the early 2000s. IFN-lambda and IFN- $\alpha$  share the common interferon-stimulated gene (ISG) induction pathway that leads to broad-spectrum antiviral activities (Figure 9). The biological activity of Lambda is derived from its recombinant human IFN  $\lambda 1$  moiety. Lambda binds to the human Type III IFN receptor leading to receptor dimerization. Receptor dimerization activates multiple intracellular signal transduction pathways initially mediated by the JAK/STAT (Janus kinase/signal transducer and activator of transcription) pathway.

## Figure 9: Mechanism Action of Type I and Type III Interferons IFN $\lambda$ and Type 1 IFNs

Lambda is a covalent conjugate of human recombinant non-pegylated IFN lambda (IFN  $\lambda$ ) and a 20-kDa linear PEG chain. Lambda has been investigated extensively in the treatment of CHB and CHC, and is now being investigated in CHD.

As of March 2017, over 3,700 subjects (including 237 healthy subjects; 197 subjects with HBV; 3,276 subjects with HCV; and 12 subjects with HDV) have received Lambda or comparator in 19 Phase 1, 2, or 3 clinical trials. These studies that have evaluated the antiviral activity of lambda IFN and chronic hepatitis B and hepatitis C infection.

In chronic HBV infection, lambda interferon was evaluated as monotherapy in a dose finding study in interferon naïve patients (LIRA-B). Subjects were randomized to receive weekly lambda 180 or 240  $\mu$ g or interferon alpha at 180  $\mu$ g for 48 weeks. The 240  $\mu$ g dose was discontinued for development during the study and only 13 patients received this dose. Hepatitis B e antigen seroconversion rates were comparable for interferon lambda and alpha groups at week 48 (17.5% versus 16.9%, respectively) however lambda noninferiority was not met at week 24 post-treatment. (13.8% versus 30.1%, respectively; lambda versus alpha 80% CI). Lambda was well tolerated at single subcutaneous doses of up to 5 mcg/kg and multiple subcutaneous doses of up to 180  $\mu$ g administered weekly for 48 weeks. Interestingly, known side-effects of interferon alpha (constitutional symptoms, neurologic events, flulike symptoms, musculoskeletal symptoms, and psychiatric events) were lower in the interferon lambda 180  $\mu$ g group (50%) compared to the IFN alpha group (72.3%).

The antiviral activity of lambda interferon against HCV has had the most extensive patient experience amounting to >3700 subjects in various phase 2 and 3 studies. In HCV, lambda interferon has been administered with various oral combination therapies including Ribavirin plus daclatasvir and Ribavirin plus asunaprevir. Treatment durations have ranged from 24-48 weeks and lambda interferon dosing has ranged from 80, 120, 184 to 240  $\mu$ g per week. In patients with HCV genotype 1 and 4 infection,

there was a significant relationship between lambda exposure (based on AUC or C Max) and undetectable HCV RNA at week 4, with the largest difference between ages and dose levels between the 120 and 180 µg exposure ranges. Episodes of anemia and neutropenia were significantly less frequent in subjects receiving lambda interferon compared to alpha interferon across all doses and exposure duration. Based on promising phase 2 HCV studies, phase 3 studies in chronic HCV infection were performed evaluating fixed 180 µg doses of lambda in combination with Ribavirin and daclatasvir and telaprevir for 24–48 weeks in genotype 1 infection and 12–24 weeks in genotype 2/3 infection.

[figure not shown]
In general, lambda interferon has been generally well tolerated by patients in clinical studies. Compared to alpha interferon, there is a lower frequency of musculoskeletal (myalgia, arthralgia, and back pain) and flu-like symptoms (chills, pyrexia, and pain) and a notable lack of hematologic toxicity in the WBC or platelet lineages in subjects receiving Lambda interferon based regimens. Laboratory abnormalities have generally been of low grade and self-limited. When study regimens included concomitant RBV administration, decreases in hemoglobin levels were observed as expected; however, anemia was less frequent and milder with Lambda/RBV than with alfa/RBV. Hematologic toxicity was also reported less frequently in groups treated with Lambda compared with alfa.

### ***Lambda Inteferon in Chronic HDV Infection***

Lambda has demonstrated in vivo activity against hepatitis D and hepatitis B viruses. In an HBV/HDV-infected human liver chimeric mouse model, Lambda reduced HDV and HBV viremia by 1.2-log and serum HBsAg level by 2.5-fold after 4 weeks of treatment. The 4 weeks of Lambda treatment also decreased intrahepatic genomic/antigenomic HDV RNA by 6.1/2.2-fold and intrahepatic HBV RNA by 8.6-fold in the mice.

In a first-in-humans for HDV, multicenter, phase 2 clinical trial, Lambda interferon monotherapy is currently being explored (NCT:02765802) in New Zealand, Pakistan and Israel. The Lambda Interferon MonoTherapy study (LIMT) study, has completed enrollment and initiation of dosing in 33 patients that are randomized to receive either 120 µg or 180 µg of weekly administered lambda interferon for 48 weeks followed by 24 weeks of post-therapy follow-up. At the AASLD liver meeting in October 2017, the study investigators reported interim results describing that 10 of 33 patients had reached 24 weeks of therapy. 6 of 10 patients were responders, achieving  $\geq 2$  log decline or below the lower limit of quantitation in HDV RNA at week 24 (Figure 9). Preliminary results also demonstrated that lambda interferon had comparable anti-HDV activity to historical peginterferon alpha at 24 weeks of therapy. These preliminary results appear comparable to peginterferon alpha therapy at similar time points where 15 of 91 subjects (16%) achieved HDV RNA negativity by week 8 and 19 of 91 subjects (21%) achieved HDV RNA negativity by week 12 of therapy in the HIDIT-2 clinical trial. Adverse effects have included grade 3 elevations in ALT in 3 patients and jaundice in 3 patients, two of which required permanent drug discontinuation and 1 required temporary interruption and resumption at a reduced dose. Constitutional symptoms were much milder and less frequent than historical data with IFN alfa.

**Figure 9: Mean viral load change from baseline to week 24 for peginterferon lambda.**

### Role of intestinal microbiome in chronic liver diseases

With increasing appreciation of the gut-liver axis, the role of the intestinal microbiome and bacterial translocation on the pathogenesis of liver disease and its progression including inflammation and fibrosis has been a recent focus of investigators.

In patients with chronic hepatitis B, investigators have described extensive differences between patients with and without cirrhosis regarding the fecal microbiota community and altered composition of intestinal Bifidobacterium with a shift from beneficial species to opportunistic pathogens in patients with cirrhosis. Further studies have described that the existence of cirrhosis (regardless of etiology) is associated with microbial dysbiosis and changes in intestinal microbial composition. Specifically, in patients with cirrhosis, pathogenic species appear to be more likely to translocate across the gut wall.

In addition to the data in cirrhotic patients, emerging data suggests bacterial translocation (BT) may occur at earlier stages of compensated liver disease and can also contribute to progression of liver disease. Kupffer cells (KC) express Toll-like Receptors (TLRs) that are highly sensitive to lipopolysaccharide LPS-triggered TLR activation. Additionally, KC, are also potent activators of hepatic stellate cells (HSC) which play a vital role in hepatic fibrogenesis. In an *in vivo* mouse model, *Seki et al* reported a mechanism that promotes the pro-fibrogenic response where LPS binds to TLR-4 on the HSC which, in turn, leads to KC chemotaxis as well as to sensitization of HSC to TGF- $\beta$  signaling. *Henao-Mejia and Elinav* in another landmark study described that bacterial translocation through TLR-4 and TLR-9 dependent pathways drove non-alcoholic fatty liver disease

(NAFLD) and its progression to steatohepatitis. These and other studies outline the role of microbial products in activation of key intracellular events involved in liver inflammation and fibrosis, thus conceptually establishing a link between BT to the portal system and liver disease progression. Other studies have also suggested that BT to the systemic circulation may occur in earlier stages of liver fibrosis. In the serum of chronic hepatitis B and C patients in different stages of liver fibrosis, elevated levels of soluble CD14 (sCD14), a macrophage-derived marker of LPS bioreactivity were identified. In addition, evidence of portosystemic shunting and decreased Kupffer cell function was described in pre-cirrhotic HCV patients using highly sensitive quantitative liver function tests and SPIO-MRI imaging respectively.

Microbiome diversity and bacterial translocation in chronic HDV patients has not been described in the literature. We plan to assess the fecal microbiota diversity and its bacterial translocation in chronic hepatic D (HDV) and their changes during treatment with lonafarnib, ritonavir and lambda. The initial focus would be to recapitulate the findings of dysbiosis seen in other liver diseases in patients with HDV.

### **HYPOTHESIS AND AIMS**

Therapy with lonafarnib plus ritonavir and lambda interferon will lead to a significant decline in hepatitis D virus levels.

### **ASSESSMENT OF RESPONSE TO THERAPY**

#### **Primary Therapeutic End Point:**

Decrease of HDV RNA by >2 log from baseline at 24 weeks of therapy with lonafarnib plus ritonavir and lambda interferon.

#### **Primary Safety End Point:**

The ability to tolerate lonafarnib plus ritonavir with lambda interferon therapy for 24 weeks of therapy. Discontinuation of the medication by the clinical team or patient will be considered a failure to tolerate the medicine.

#### **Secondary End Points:**

1. Sustained undetectable HDV RNA in serum at weeks 12 and 24 post treatment follow up.
2. Reduction in histologic inflammatory scores (modified HAI) by at least two points with no progression in histologic fibrosis (Ishak) at week 24 post-treatment follow-up.
3. Normalization of serum ALT (ALT <20 in females and ALT <31 in males) at the end of therapy, at week 12 of post-therapy follow-up and at week 24 of post-therapy follow-up, OR reduction in serum ALT by >50% of baseline at week 12 of post therapy follow up and week 24 of post therapy follow up.
4. Reduction in hepatic venous pressure gradient (HVPG) measurements by >25% of baseline OR normalization of HVPG (<5 mm Hg) at end of therapy.
5. Reduction in Fibroscan® transient elastography values by >25% of baseline at end of therapy.

6. Loss of HBsAg from the serum at the end of therapy, at week 12 of post-therapy follow-up or at week 24 of post-therapy follow-up.
7. Changes in quantitative HBsAg levels at the end of therapy and at week 24 of post therapy follow up, compared to baseline.
8. Changes in symptom scale measurements and quality of life before, during and after therapy.
9. Changes in the fecal microbiome before and after treatment.

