***PRECIS***

Chronic delta hepatitis is a serious form of chronic liver disease caused by infection with the hepatitis D virus (HDV), a small RNA virus that requires farnesylation of its major structural protein (HDV antigen) for replication. Based on previous and ongoing clinical trials demonstrating effectiveness against HDV, we propose to treat 26 adult patients with chronic delta hepatitis using the combination of the farnesyltransferase inhibitor (FTI) lonafarnib (LNF), the protease inhibitor ritonavir (RTV) and peginterferon lambda-1a(lambda). In this phase 2a open label study, the safety and antiviral effects of triple therapy with LNF, RTV and lambda for a period of 6 months. After dosing, all patients will be monitored for 24 weeks off therapy. Nucleos(t)ide analogue therapy will be instituted/continued during this study to prevent the possibility of HBV reactivation/flare for the duration of participation in this clinical trial. Patients with quantifiable HDV RNA in serum will be enrolled. At each clinic visit, patients will be questioned about side effects, symptoms and quality of life, undergo focused physical examination, and have blood drawn for complete blood counts, HDV RNA, and routine liver tests (including ALT, AST, alkaline phosphatase, direct and total bilirubin, and albumin). At the end of the treatment, patients will be admitted to the clinical center and will undergo repeat liver biopsy and HVPg measurements, repeat physical examination, assessment of symptoms (using a symptom scale questionnaire), complete blood counts, routine liver tests, and hepatitis B and D viral markers. The primary therapeutic endpoint will be a decline of HDV RNA viral titer of 2 logs at the end of therapy. The primary safety endpoint will be the ability to tolerate the drugs at the prescribed dose for the full course of therapy. This clinical trial is designed as a phase 2a study assessing the antiviral activity, safety and tolerance of fixed doses of lonafarnib, ritonavir and peginterferon lambda.

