## **STUDY PROCEDURES AND SCHEDULE**

This is an open-label clinical trial treating 26 adult patients with chronic delta hepatitis with lonafarnib plus ritonavir and lambda interferon for 24 weeks. Patients will undergo baseline testing including blood draws, imaging, safety consults, and liver biopsy with portal pressure measurements prior to starting therapy. During therapy, all patients will be monitored with quantitative HDV RNA and HBV DNA levels as well as routine safety measures and liver function tests. After 24 weeks, therapy will be stopped and patients will again undergo repeated testing including blood draws, imaging, and safety consults. After stopping therapy, patients will be followed for an additional 24 weeks. At the end of the 24 weeks of post-therapy follow-up, patients will be re-admitted to the NIH Clinical Center and will undergo repeat testing including blood draws, imaging, as well as a transjugular liver biopsy with hepatic venous pressure gradient measurements.

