## LABORATORY PROCEDURES/EVALUATIONS

- **Baseline Labs** - prothrombin time (PT/INR), partial thromboplastin time (PTT), reticulocyte count, plasma haptoglobin level, anti-HBc.
- **Routine Labs** - complete blood count (CBC with differential), acute care panel (sodium, potassium, chloride, bicarbonate, creatinine, glucose, urea nitrogen, eGFR ), mineral panel (albumin, calcium, magnesium, phosphorus), hepatic panel (alkaline phosphatase, ALT, AST, total bilirubin, direct bilirubin), lipid panel (total cholesterol, triglycerides, HDL, LDL), LDH, CK, serum uric acid and total protein, urinalysis.
- **Monthly Labs** - PT, thyroid panel, pregnancy test
- **Serology Labs** - HBsAg, anti-HBs, HBeAg, and anti-HBe, anti-HDV, quantitative HBsAg levels.
- **Pancreatitis Monitoring:** amylase, lipase
- **Viral Kinetic and Pharmacokinetic Assessment (VK and PK):** includes HDV RNA and HBV DNA qualitative tests via polymerase chain reaction assay (PCR) or a quantitative PCR (qPCR) for viral titer. One red top tube (10 mL) will be obtained and stored in -80 for pharmacokinetic (PK) analysis of lonafarnib, ritonavir and lambda.

- **Reproductive Panel** - In males, AM levels of inhibin B, luteinizing hormone (LH), total and free testosterone, and follicle stimulating hormone (FSH) will be obtained. In females, AM levels of luteinizing hormone (LH), estradiol, progesterone, antimullerian hormone, follicle-stimulating hormone (FSH), dehydroepiandrosterone (DHEA), dehydroepiandrosterone sulfate (DHEAS), testosterone, sex hormone binding globulin (SHBG) and 17-hydroxyprogesterone (17-OHP) will be obtained.
- **Immunological Studies** - 30 - 50 ml of whole blood will be collected for immunological studies at specified time points described in table 1. 5 mm of liver tissue at baseline and end of therapy will also be collected for immunological studies, provided sufficient liver tissue is available after the required amount is obtained for histopathology. An additional pass will not be performed to obtain additional tissue for immunological studies.
- **Research Blood for Storage** - 7 ml of serum will be collected and stored at -80° C in the NIDDK clinical core lab.

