13. EKG

### **End of Therapy**

At the end of therapy (week 24), patients will be seen at the NIH Clinical Center for an evaluation as follows:

1. Continuation of HBV therapy
2. Discontinuation of study therapy
3. MD Visit
4. Monitoring of vital signs and weight (>10% weight loss from baseline would result in a follow-up nutrition consult).
5. Routine labs
6. Pancreatic labs
7. Serology
8. Baseline labs
9. Monthly labs
10. Consults
11. Reproductive labs
12. Immunological testing
13. Viral kinetics, pharmacokinetics and blood for storage
14. Microbiome
15. Imaging
16. Fibroscan

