**Post Treatment Week 24**

At the end of study followup (week 24 post treatment), patients will be readmitted to the NIH Clinical Center for an evaluation as follows:

1. Continuation of HBV therapy
2. MD Visit

3. Monitoring of vital signs and weight (>10% weight loss from baseline would result in a follow-up nutrition consult).
4. Routine labs
5. Pancreatic labs
6. Serology
7. Baseline labs
8. Monthly labs
9. Consults
10. Reproductive labs
11. Immunological testing
12. Viral kinetics, pharmacokinetics and blood for storage
13. Microbiome
14. Imaging
15. Fibroscan

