16. EKG
17. Liver biopsy

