3. ***The risks of hepatic venous pressure gradient (HVPG) measurements:*** The hepatic venous pressure gradient (HVPG) will be measured during transjugular liver biopsy as a combined procedure in patients that participate in this study. Portal pressure measurements will not be performed if the patient has evidence of coagulopathy unresponsive to vitamin K (INR >1.5) or low platelets (Platelets < 50,000 k/uL) which may place them at a potentially higher risk for bleeding. Portal pressure measurements will be repeated at the end of therapy (week 24). This will be done as a direct measure for portal hypertension and is expected to provide a more dynamic, functional assay of the direction of change in liver disease to follow the evolution of disease and the need for additional clinical intervention. Portal pressure measurements were initially used as a diagnostic test for portal hypertension and as part of the work up of patients with chronic liver diseases. Normal gradients are less than 5mmHg. It is accepted that decreasing the gradient to 12 mmHg or less will prevent variceal bleeding. It has also become clear that portal pressures convey prognostic information, which is an independent predictor of mortality in patients with liver disease related to cirrhosis. The commonest current use in North America for portal pressure measurements is related to placement of transjugular intrahepatic portosystemic shunts by interventional radiology.

There are various ways to measure portal pressure. The simplest and safest way is by measuring the hepatic venous wedged pressure with a balloon catheter and subtracting the free hepatic vein pressure to obtain a gradient. The main drawback of this technique is that presinusoidal portal hypertension may be underestimated. The hepatic venous pressure gradient is the current standard for measuring portal pressures.

Hepatic venous pressure gradient measurements are typically performed by interventional radiologists. They are normally performed as combined procedures along with a liver biopsy to further aid in staging of liver disease. Aside from the

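### The repeat HVPG has two conflicting times, and on the visit schedule secondary endpoint 4 has no value at end of therapy

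*Combined protocol and SAP*

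**What the plan says.** **Sections that put the repeat at end of therapy**

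- Secondary End Points, item 4: "Reduction in hepatic venous pressure gradient (HVPG) measurements by >25% of baseline OR normalization of HVPG (<5 mm Hg) at end of therapy".
- Precis: "At the end of the treatment, patients will be admitted to the clinical center and will undergo repeat liver biopsy and HVPg measurements".
- Hazards and Discomforts, item 3: "Portal pressure measurements will be repeated at the end of therapy (week 24").
- Laboratory Procedures/Evaluations, on immunology tissue only, with no mention of HVPG: "5 mm of liver tissue at baseline and end of therapy will also be collected for immunological studies".

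**Sections that put it at the end of post-treatment follow-up**

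- Study Procedures and Schedule: after 24 weeks of follow-up off therapy, patients return for repeat testing "as well as a transjugular liver biopsy with hepatic venous pressure gradient measurements". For the end of treatment the same paragraph mentions bloods, imaging and consultations, but no biopsy and no HVPG.
- Table 1: the row for biopsy with portal pressure is marked at baseline and at week 48 only.
- Post Treatment Week 24: the visit list ends with "17. Liver biopsy". It does not name HVPG.

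Secondary endpoint 2 (histology) is set at week 24 of post-treatment follow-up.

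**The concern.** An endpoint can be analysed as defined only if the measurement is scheduled at the time in its definition. Here the definition points to one visit and the operative schedule to another, 24 weeks apart, and nothing in the protocol says which text controls. A change in portal pressure at the end of active treatment and a change after 24 weeks without treatment answer different questions. If the time is left open, it may be chosen after the data are seen, or the week-48 value may be reported under an end-of-therapy label.

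Histology and HVPG come from the same procedure, so the conflict reaches further than one endpoint. With a single repeat procedure, endpoint 2 (post-treatment week 24) and endpoint 4 (end of therapy) cannot both be measured at their stated times.

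**Working it through.** The protocol states no figure to reproduce. The check is a cross-reading of the sections, with simple counts.

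**1. Is HVPG tied to the biopsy?** Yes. Hazards and Discomforts, item 3, describes it as measured in a combined procedure with the transjugular biopsy. A visit without a scheduled biopsy therefore has no scheduled HVPG.

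**2. What does Table 1 schedule?** The biopsy and portal pressure row, read across the eight time columns:

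| Baseline | Day 0 | Wk 1-3 | Wk 4-20 | Wk 24 | Wk 25-26 | Wk 28-44 | Wk 48 |
|---|---|---|---|---|---|---|---|
| yes | - | - | - | - | - | - | yes |

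The row gives one HVPG at baseline, none at week 24 and one at week 48.

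**3. Is the absence at week 24 just a shortened list?** The two visit lists were compared item by item. The week-24 list opens "At the end of therapy (week 24), patients will be seen at the NIH Clinical Center for an evaluation as follows" and the later one opens "At the end of study followup (week 24 post treatment), patients will be readmitted to the NIH Clinical Center for an evaluation as follows".

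- End of Therapy: 17 items.
- Post Treatment Week 24: 17 items.
- Shared: 16.
- Only at end of therapy: stopping study treatment.
- Only at post-treatment week 24: the liver biopsy.

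The lists otherwise match, so the biopsy looks deliberately placed at the later visit. The later visit is also the one described as a readmission, which fits a procedure that Hazards and Discomforts follows with 24 hours of observation.

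**4. What does endpoint 4 need, and what does it get?** It needs a baseline value and an end-of-therapy value. On the schedule it has a baseline value and a week-48 value. Scheduled HVPG at the stated time: 0 of the 26 planned patients. Distance from the stated time to the only repeat: 48 - 24 = 24 weeks.

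**5. How is the text divided on HVPG itself?** Three places support end of therapy: endpoint 4, the Precis and the HVPG risk paragraph. Two support study week 48: the design narrative and Table 1. The post-treatment week 24 list supports week 48 for the biopsy only, and the immunology paragraph supports week 24 for tissue only.

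**6. What happens under each reading with one repeat procedure?**

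| Text followed | Endpoint 2 (histology, post-treatment wk 24) | Endpoint 4 (HVPG, end of therapy) |
|---|---|---|
| Design narrative and Table 1 | measured on time | no value at stated time |
| Precis and HVPG risk paragraph | no tissue at stated time | measured on time |

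**The case against.** The strongest reply is that two repeat procedures may be intended, one at week 24 for endpoint 4 and one at week 48 for endpoint 2. No section rules this out, and the design narrative's account of week-24 testing is worded as an open list. But no section describes two repeats; the Precis and Table 1 each show only one. Even on this reading, the End of Therapy list and Table 1 are wrong at week 24. The defect would then be an omission, and it would still need correcting.

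A second reply is that the end-of-therapy phrase in endpoint 4 may attach only to the normalization limb. That limb would still have no scheduled value, and the 25% reduction limb would have no stated time at all. The conflict between the Precis and risk paragraph on one side and the design narrative and Table 1 on the other would remain.

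A third reply is that the operative texts agree with each other, so sites would follow the schedule and data would be collected. This is fair as a prediction of conduct. It makes it more likely that the repeat occurs at week 48, which is exactly the case in which endpoint 4 has no value at its stated time.

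It is also true that end-of-therapy timing could be deliberate, since the Fibroscan endpoint is set there. That is weak evidence, because Fibroscan is scheduled at both visits. Finally, a biopsy done to work up a liver event could fall near week 24, but it is event-driven and need not include HVPG.

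**Conclusion.** The concern holds. The protocol gives two times for the repeat HVPG, 24 weeks apart. Under its visit lists and Table 1, secondary endpoint 4 has no scheduled measurement at end of therapy in any patient.

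The statement that endpoints 2 and 4 cannot both be met rests on there being one repeat procedure, which is all that any section describes. The statement that endpoint 4 is unscheduled at week 24 does not need that assumption. The documents do not settle which time was intended.

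The damage is confined to secondary endpoints and to the liver tissue planned for immunology. The correction should be made before analysis, but the primary endpoints and the sample size stand as they are.

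**What to change.** State one intended time for the repeat HVPG and bring these places into line with it: the Precis; Secondary End Points item 4; Study Procedures and Schedule; the immunology paragraph; the End of Therapy and Post Treatment Week 24 lists; Table 1; and Hazards and Discomforts item 3.

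- **(a) If the design narrative and Table 1 stand:** define endpoint 4 at post-treatment week 24 (study week 48), the same visit as endpoint 2. Describe it as an off-treatment effect, name HVPG in that visit's list, and align the Precis, the immunology paragraph and the risk paragraph. This changes text only and adds no procedure. The price is that endpoint 4 no longer measures an end-of-treatment effect and no longer shares its time with the Fibroscan endpoint.
- **(b) If week 24 was intended:** correct the design narrative, the End of Therapy list and Table 1, and state how endpoint 2 obtains histology at post-treatment week 24. If the week-48 biopsy is kept as well, there are two repeat procedures. The 2.5 rem exposure figure in Hazards and Discomforts item 4 would then need checking, because the protocol does not say how many procedures it covers.

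Under either route, also state the denominator for endpoint 4. The section on patients discontinuing therapy already counts those who stop or drop out as treatment failures. It does not cover patients whose HVPG is missing because a percutaneous biopsy was substituted or because the measurement was withheld for coagulopathy or low platelets.

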### **Design of the Trial/Statistical considerations**

This study is designed as a phase 2a FDA regulated clinical study evaluating the utility of combination triple therapy of lonafarnib, ritonavir and lambda interferon in patients with chronic HDV infection. This study should show if HDV suppression is possible; assist in suggesting if this dose is effective for viral suppression; and how well lonafarnib, ritonavir and lambda interferon are tolerated. Thus, assessment of virologic response is the primary therapeutic endpoint and safety/tolerability is the primary safety endpoint.

Measurement of HDV RNA levels will be performed in two batches, the first batch will be analysed after the last patient has completed treatment, and the second batch when the last patient completes post-therapy follow-up.

In order to achieve a primary virologic response goal of a 2-log decline in HDV RNA in serum at end of 24 weeks of therapy, a total of 26 patients will be enrolled. This designation was made based on a power calculation with a statistical power designated at 0.9, alpha at 0.05, and two tailed testing, the effect size was found to be -1.1.

$$effect\ size = \frac{2672.231 - 267223.1}{240500.8} = -1.1$$

Based off prior interferon based studies, we would also include a potential drop out rate of 30%. Thus, the sample size desired will be 26 subjects.

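### HVPG and Fibroscan are defined only as responder outcomes in a single arm with no reference rate; the paired change from baseline should be added as the analysed quantity

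*Combined protocol and SAP*

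**What the plan says.** Under Secondary End Points, item 4 is "Reduction in hepatic venous pressure gradient (HVPG) measurements by >25% of baseline OR normalization of HVPG (<5 mm Hg) at end of therapy" and item 5 is "Reduction in Fibroscan® transient elastography values by >25% of baseline at end of therapy". Neither item lists the change itself. Item 7, by contrast, is written as a change: "Changes in quantitative HBsAg levels at the end of therapy and at week 24 of post therapy follow up, compared to baseline".

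Hazards and Discomforts, item 3, explains why HVPG is repeated: it "is expected to provide a more dynamic, functional assay of the direction of change in liver disease". The same item gives 5 mm Hg as the upper limit of normal and 12 mm Hg as the level relevant to variceal bleeding. It does not discuss 25%.

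Study Procedures and Schedule describes one treated group: "This is an open-label clinical trial treating 26 adult patients with chronic delta hepatitis with lonafarnib plus ritonavir and lambda interferon for 24 weeks". Design of the Trial/Statistical considerations deals only with HDV RNA. It gives no test, interval, reference rate, SD or expected change for any secondary endpoint.

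**The concern.** A responder proportion in an uncontrolled study means something only against a rate expected without treatment, and none is given here. Some patients will cross a 25% threshold through measurement variation alone, so a modest count cannot be told from noise. The paired change has a natural reference value, zero, and uses the size and direction of every patient's change, which is the protocol's stated reason for measuring HVPG.

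The second limb of item 4 adds a separate difficulty. The Inclusion and Exclusion Criteria set no minimum baseline HVPG. Read literally, a patient who starts in the normal range and stays there is a responder.

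At stake is whether two secondary endpoints, one resting on an invasive procedure, can be interpreted at the end of the study.

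**Working it through.** **The plan's own figure.** The effect size is (2672.231 − 267223.1)/240500.8 = −1.10. The usual normal formula, 2(1.960 + 1.282)²/1.1² = 17.4, gives 18, and 18/0.70 = 25.7 gives 26. This matches "a total of 26 patients will be enrolled", using the per-group n of a two-group formula. It concerns HDV RNA only and says nothing about HVPG or stiffness. I use n = 26 (no loss) and n = 18 (26 × 0.70 = 18.2).

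**Assumptions.** The documents give no SD, expected change or measurement error for either measure. I take the within-patient log change as normal with SD *s* from 0.20 to 0.40 and true mean falls *r* of 10% to 30%.

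**Responders from noise alone.** With no true change, P(fall >25%) = Φ(ln 0.75/*s*), where ln 0.75 = −0.2877.

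| *s* | ln 0.75/*s* | P(fall >25%) | expected of 18 | expected of 26 |
|---|---|---|---|---|
| 0.20 | −1.438 | 0.075 | 1.4 | 2.0 |
| 0.25 | −1.151 | 0.125 | 2.2 | 3.2 |
| 0.30 | −0.959 | 0.169 | 3.0 | 4.4 |
| 0.40 | −0.719 | 0.236 | 4.2 | 6.1 |

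At *s* = 0.30 the chance of at least 3 apparent responders among 18, with no effect, is 61%. An observed 5 of 18 has an exact 95% CI of 10% to 53%.

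**The below-5 limb of HVPG.** Assume no true change and an SD of 1 to 2 mm Hg for the difference between two readings. The probability of ending below 5 mm Hg from baseline *b* is Φ((5 − *b*)/SD). For *b* = 4 it is 84% (SD 1) or 69% (SD 2). For *b* = 6 it is 16% or 31%. At both baselines the below-5 limb already contains every fall of more than 25%, so these are the full item 4 rates.

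**Illustrative power, 25% cut only.** The paired t test is two-sided at 0.05 (noncentral t), with δ = −ln(1 − *r*). The cut is tested by an exact one-sided 0.025 binomial test of p₁ = Φ((ln 0.75 + δ)/*s*) against its own no-effect rate from the first table. This is generous to the cut, because that rate is not known in this trial.

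Worked case, *s* = 0.30, *r* = 0.20, n = 18: δ = 0.223; noncentrality = 0.223 × √18/0.30 = 3.16; paired power 0.845. For the cut, p₁ = 0.415, reject at 7 or more of 18, power 0.674. The gain is 17 points.

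Paired test vs cut at n = 18 (gain in points):

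| *s* | 15% fall | 20% fall | 30% fall |
|---|---|---|---|
| 0.20 | 0.901 vs 0.543 (36) | 0.994 vs 0.862 (13) | about 1 vs about 1 (0) |
| 0.25 | 0.739 vs 0.497 (24) | 0.946 vs 0.787 (16) | about 1 vs 0.995 (<1) |
| 0.30 | 0.582 vs 0.409 (17) | 0.845 vs 0.674 (17) | 0.997 vs 0.975 (2) |
| 0.40 | 0.370 vs 0.201 (17) | 0.607 vs 0.375 (23) | 0.945 vs 0.796 (15) |

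Over *s* of 0.20 to 0.40, falls of 10% to 30% and both sample sizes, the gain runs from 0 (for example *s* = 0.20, 30% fall) to 41 points (n = 26, *s* = 0.20, 10% fall: 0.733 vs 0.327). None of this covers the below-5 limb of item 4.

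**HVPG timing.** The Precis, Secondary End Points item 4 and Hazards and Discomforts item 3 put the repeat HVPG at the end of therapy (week 24). Study Procedures and Schedule puts it at 24 weeks after therapy. The End of Therapy visit list has no biopsy or HVPG, the Post Treatment Week 24 list has the biopsy, and Table 1 shows the repeat biopsy with portal pressures only at week 48. As scheduled, item 4 has no end-of-therapy measurement. Fibroscan is scheduled at week 24, so item 5 does not have this problem.

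**The case against.** Four fair points can be made in favour of the plan.

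First, a reader might infer that the plan gives up a definite amount of power, such as 12 to 36 points. The documents do not support that. No test of these endpoints is planned, so there is no planned power to lose. The SD, the effect and the null are all assumed, and the gain nearly vanishes when the true fall is large and the SD small. Part of the 36-point case comes from the discreteness of the binomial test, whose attained one-sided level there is 0.009 rather than 0.025. Against a fixed outside reference rate the sign can even reverse. This point stands, and the power figures are illustration only.

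Second, a reader might infer that the measured change will be discarded. That also goes too far. The section defines endpoints, the values are collected, and nothing prevents their being reported. What can be said is that the change is not listed and the analysis is unspecified.

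Third, items 4 and 5 might be read as out of line with the rest. They are not: items 1, 2, 3 and 6 and the primary endpoint are also response definitions. Nor is the lack of a citation for 25% an error in itself.

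Fourth, Monitoring of Patients Discontinuing Therapy counts those who stop or drop out as treatment failures. A responder rate can carry all 26 patients on that rule; a paired change cannot. Zero is also an imperfect null without a control, because regression to the mean and time trend remain. Both limits are real. They are reasons to keep the responder count beside the change, not to report it alone.

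**Conclusion.** The point holds as a gap in definition and prespecification for two secondary endpoints. They are responder outcomes only, in one arm, with no reference rate and no change from baseline listed. Under the assumed log-change SDs, noise alone would yield 7.5% to 24% responders on the 25% cut. Item 4 can also be met without improvement by a patient who starts below 5 mm Hg; that follows from the wording and the entry criteria and needs no assumption about variability.

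The direction of the power comparison favours the paired change throughout the range examined when the cut is tested against its own no-effect rate. Its size is not a property of this plan. The primary endpoint and its sample size are unaffected. The change is worth making because it costs little and uses data already scheduled, subject to settling when HVPG is measured.

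**What to change.** - For items 4 and 5, at the stated timepoint, specify the within-patient change from baseline: liver stiffness on the log scale, and HVPG on one scale chosen in advance. Report the estimate with a 95% CI and one named paired test for each.
- Keep the responder counts as descriptive, with exact 95% CIs and with patients who stop or drop out counted as failures, as the protocol already provides.
- Show the below-5 limb of item 4 separately, for patients whose baseline HVPG is 5 mm Hg or more.
- Reconcile the passages that place the repeat HVPG at end of therapy with those that schedule it at post-treatment week 24, so that item 4 names a timepoint at which it is measured.
- State that the paired analysis uses only patients with both measurements, give that number, and say that without a control it cannot separate treatment effect from regression to the mean or time trend.

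The first, second, third and fifth changes are wording and analysis text only and add no patients or procedures. The statistical price is the loss of patients without a second measurement, including failed Fibroscan readings, which the protocol puts at 5 to 10 percent of persons.
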